APPENDIX 1. CONCOMITANT MEDICATIONS AND SUPPLEMENTS

Note: Also see Section 6.3.2.

Use of the following is prohibited from the Screening Visit through the Follow-up Visit, unless noted otherwise below:

- Specific inhibitors of PDE5, including sildenafil, tadalafil, vardenafil
- Nonspecific inhibitors of PDE5, including dipyridamole, theophylline
- Any supplement for the treatment of erectile dysfunction
- Other sGC stimulators, including riociguat and vericiguat
- Nitrates such as nitroglycerin, isosorbide mononitrate, isosorbide dinitrate, sodium nitroprusside, amyl nitrate

Note: Participants taking arginine or citrulline for the treatment of mitochondrial disease will be allowed to continue these therapies.

- Aspirin \geq 325 mg/day
- Any anticoagulant medication
- Any P2Y12 inhibitor, including cangrelor, clopidogrel, prasugrel, ticagrelor, ticlopidine
- Use of any “illicit drug” is not permitted beginning 1 month before Screening through the Follow-up Visit

Note: Use of cannabis and cannabidiol products for medical purposes is permitted, except for 24 hours before the Screening, Day 1, and EOT visits, and for 4 hours prior to all other study visits.

- [REDACTED]
- [REDACTED]
- [REDACTED]
- [REDACTED]
- [REDACTED]

Cyclerion Therapeutics, Inc.

C6463-201

*Phase 2a safety, tolerability, pharmacokinetic, and pharmacodynamic study
in individuals with mitochondrial encephalomyopathy, lactic acidosis, and
stroke-like episodes (MELAS)*

21 March 2022

Statistical Analysis Plan

Version 2

MODIFICATION HISTORY

Version 2 of this SAP was created to align with changes made in C6463-201 Protocol Amendment 2, dated 23 April 2021 and Amendment 3, dated 23 July 2021. Major changes made to this SAP are summarized below.

[figure not shown]
Item	Section(s)	Description of Change(s)
1	1 (Introduction)	Updated to reflect the current version of the protocol, C6463-201 Protocol Amendment 3, dated 23 July 2021.
2	3.1 (Overall Study Design and Plan)	Figure 1 was replaced with the updated figure in Protocol Amendment 3
3	16.1 Schedule of event	Table 3 was replaced with the updated table in Protocol Amendment 3
4	3.2.2 (Exploratory Endpoints)	Updated to reflect Protocol Amendment 3
5	4.3.3	Updated definition of PD Evaluable Population
6	5.1 (Disposition), 5.2 (Protocol Deviations)	Inserted phrase 'if applicable' for summaries related to the PD Evaluable population
7	7.2.2 (Compliance)	Revised text from Compliance is defined as the total doses taken divided by the total doses expected to be taken, times 100. to Compliance is defined as the total dosage taken divided by the total dosage expected to be taken, times 100.
8	9.1.8 Adverse Events of Special Interest	Updated text to clarify that AESIs will be presented as collected in the eCRFs, and removed Table 1 (Criteria for AESIs) to be consistent with Protocol Amendments 2 & 3
9	9.2 (Clinical Laboratory)	For urinalysis, summary tables will be performed as data permit.
10	9.3 (Vital Sign Measurements)	Added descriptive statistics for change from baseline in SBP, DBP, MAP, and PCI criteria for standing and orthostatic SBP, DBP, and pulse.
11	10 (Questionnaires)	Revised analyses to be conducted on the safety population instead of the PD evaluable population.
12	11 (PK)	Revised imputation of BLQ values for calculation of summary statistics. Also included additional text from protocol.
15	12. (PD)	Clarified endpoints to be summarized and those presented only in listings

Table of Contents

List of Abbreviations.....	5
1. Introduction	7
2. Objectives	7
2.1. PRIMARY OBJECTIVE	7
2.2. EXPLORATORY OBJECTIVES.....	7
3. Investigational Plan	8
3.1. OVERALL STUDY DESIGN AND PLAN	8
3.2. STUDY ENDPOINTS.....	8
3.2.1. Primary Endpoint	8

Study C6463-201 is an open-label, single-arm study in approximately 20 participants diagnosed with mitochondrial encephalomyopathy, lactic acidosis, and stroke-like episodes (MELAS) to assess the safety, tolerability, pharmacokinetics (PK) and pharmacodynamics (PD) of IW-6463 administered daily for up to 29 days.

The statistical analysis plan (SAP) provides a more technical and detailed elaboration of the data presentations and statistical analyses of the efficacy and safety data as specified in the final protocol for Study C6463-201 (C6463-201 Protocol Amendment 3, dated 23 July 2021). Specifications for tables, figures, and data listings are contained in a separate document.

2. Objectives

2.1. Primary Objective

The primary objective of the study is to evaluate the safety and tolerability of IW-6463 when administered to participants with MELAS.

2.2. Exploratory Objectives

The exploratory objectives of the study are as follows:

- To evaluate the PK of IW-6463 when administered to participants with MELAS.
- To evaluate the effect of IW-6463 on exploratory plasma biomarkers in participants with MELAS.
- To evaluate the effect of IW-6463 on CBF in participants with MELAS.
- To evaluate the effect of IW-6463 on brain activity as measured by functional magnetic resonance imaging (fMRI) in participants with MELAS.
- To evaluate the effect of IW-6463 on brain metabolites as measured by magnetic resonance spectroscopy (MRS).
- To evaluate the effect of IW-6463 on fatigue as measured by the Modified Fatigue Impact Scale (MFIS).
- To evaluate the effect on IW-6463 on cognitive function as measured by the Patient-Reported Outcomes Measurement Information System (PROMIS) Item Bank v2.0–Cognitive function.

[figure not shown]
3. Investigational Plan

3.1. Overall Study Design and Plan

C6463-201 is an open-label, single-arm study evaluating the safety, tolerability, PK, and PD of IW-6463 when administered for up to 29 days to participants diagnosed with MELAS. Because this is the first study evaluating IW-6463 in a patient population, the primary objective is safety and tolerability; see Section 2 and Section 3.2 for a complete list of study objectives and their corresponding endpoints.

To complete the study, each participant will progress through 3 distinct periods as described below. For details regarding the timing of the specific procedures and assessments, see the Schedule of Events (Table). A study schematic is shown in **Figure 1**.

Figure 1: Study Schematic

All participants will receive open-label IW-6463 once daily for up to 29 days during the Treatment Period.

* Screening assessments may take place over more than 1 day. However, all Screening procedures must be completed at least 10 but not more than 28 days before the start of the Treatment Period.

** The Day 8, Day 15, and Follow-up visits can be conducted either at home or in the study clinic, per participant/Study Center preference.

3.2. Study Endpoints

3.2.1. Primary Endpoint

The primary endpoints of the study are as follows:

- Number of participants with study drug dose reductions or discontinuations due to ≥ 1 treatment-emergent adverse event (TEAE)
- Incidence and severity of AEs

3.2.2. Exploratory Endpoints

The exploratory endpoints of the study are as follows:

- Plasma and cerebral spinal fluid (CSF) concentrations of IW-6463 as data permit at assessed timepoints.
- PK parameters as data permit, including but not limited to area under the concentration-time curve from time zero (predose) to 24 hours postdose (AUC_{tau}), maximum observed plasma concentration (C_{max}), time to C_{max} (T_{max}), apparent terminal half-life ($t_{1/2}$), plasma concentration observed at the end of a dosing interval (C_{trough}), apparent total plasma clearance (CL/F), apparent volume of distribution (V_z/F), and CSF: plasma concentration ratio.
- Change from baseline in plasma biomarker concentrations on Day 29. [REDACTED]
[REDACTED]
[REDACTED]
[REDACTED]
[REDACTED]
- Change from baseline in CBF as measured by arterial spin labeling (ASL) on Day 29
- Change from baseline in fMRI-blood-oxygen-level-dependent (BOLD) signals during resting state and a visual stimulus on Day 29, as data permit.
- Change from baseline in brain metabolite [REDACTED] levels by H-MRS on Day 29.
- Change from baseline in MFIS scores (total, physical, cognitive, and psychosocial subscores) on Day 29.
- Change from baseline in PROMIS Item Bank v2.0–Cognitive function total score on Day 29.

3.3. Treatments

All eligible participants will receive open-label IW-6463 at a starting dose of 15 mg once a day (QD). Participants will be instructed to take IW-6463 once per day on Days 2 through 28 at a time consistent (preferably ± 1 hour) with the in-clinic study drug administration on Day 1.

Exception>Note: For the Day 8, 15, and 29/ End of Treatment (EOT) visits, participants will take their dose during the visit to allow for the appropriate timing of pre- and post-

dose assessments. Attempts should be made to schedule the Day 8 and 15 visits (at home or in clinic) such that dosing can still occur at approximately the same time as the Day 1 and subsequent doses.

Participants are to record the date and time of each at-home dose administration in their diary.

3.4. Dose Adjustment/Modifications

The decision to de-escalate IW-6463 dosing in an individual participant will be made jointly by the Investigator and PPD Medical Monitor, on a per-participant basis.

Participants who require a dose adjustment from the 15-mg QD dose will be de-escalated to a 10-mg QD dose. Initiation of the new dose level should occur only after the Treatment-emergent AE(s) prompting the dose reduction has/have resolved or has improved to be considered mild in severity.

If the 10-mg IW-6463 QD dose is not tolerated, the participant will be discontinued from study drug.

4. General Statistical Considerations

Continuous variables will be summarized using the following descriptive statistics: n, mean, median, standard deviation, minimum, maximum. For the summary of continuous clinical outcomes, vital signs, and PD data, the 95% confidence intervals (CI) will also be presented. For the summary statistics of all numerical variables, unless otherwise specified, minimum and maximum will be displayed to the same level of precision as reported. Mean and median will be displayed to one level of precision greater than the data collected. Standard deviation will be displayed to two levels of precision greater than the data collected.

Categorical and count variables will be summarized by the number of participants (n) and the percent of participants in each category. Percentages will be presented as whole numbers. When count data are presented, the percentage will be suppressed when the count is zero. A row denoted “Missing” will be included in count tabulations only if there are missing values. The denominator for all percentages will be the number of participants within the population of interest, unless otherwise specified.

Baseline will be defined as the last non-missing assessment before administration of study drug on Day 1, unless otherwise specified.

4.1. Sample Size

A maximum of 20 participants will be assigned to receive IW-6463 such that approximately 12 evaluable participants complete the study.

The sample size selected is not based on statistical considerations. A sample size of approximately 12 evaluable participants in a rare disease indication is considered sufficient to address the primary and research objective.

4.2. Randomization, Stratification, and Blinding

Not applicable.

4.3. Analysis Population

4.3.1. Screened Population

The Screened population will include all participants who sign the informed consent form (ICF).

4.3.2. Safety Population

The safety population will include all participants who sign the ICF and take at least 1 dose of study drug.

4.3.3. PD Evaluable Population

The PD evaluable population will include all participants who complete the baseline and EOT Visit assessments, have $\geq 80\%$ compliance with study drug dosing, and do not have any major protocol violation(s) that could affect their PD assessment. The PD Evaluable population will be defined only if at least 12 participants are enrolled in the study.

4.3.4. PK Evaluable Population

The PK Evaluable population will include all participants who complete the EOT Visit and have ≥ 1 evaluable post-dose PK assessment.

5. Participant Disposition

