8.6. PK Evaluations (Plasma and CSF)

PK samples will be collected as scheduled in [Table 1](#). The actual date and time (24-h clock time) of each sample collection will be recorded in the source documents and eCRF. Each sample will be divided into 2 aliquots (1 each for PK and a back-up). Specific instructions for the collection and handling of biological samples are provided in the study's laboratory manual.

- Sparse whole-blood samples of approximately 2 mL will be collected for measurement of plasma concentrations of IW-6463 using a validated liquid chromatography-tandem mass spectrometry bioanalytical method.
- From each participant who does not withhold consent for the procedure, a CSF sample of approximately 4 mL will be collected for measurement of IW-6463 CSF concentration using a validated liquid chromatography-tandem mass spectrometry bioanalytical method.

The timing of sampling may be altered during the course of the study based on emerging data (eg, to obtain data closer to the time of peak plasma concentrations) to ensure appropriate monitoring. Samples collected for analyses of IW-6463 concentration may also be used to evaluate safety aspects related to concerns arising during or after the study.

Biological samples collected from participants in this study may be stored for future analysis for not more than 5 years.

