9.3.2. Populations for Analyses

Analysis populations are defined as follows.

Population	Description
Screened	All participants who sign the ICF
Safety	All participants who sign the ICF and take ≥ 1 dose of study drug
PD Evaluable	All participants who complete the baseline and EOT Visit assessments, have $\geq 80\%$ compliance with study drug dosing, and do not have any major protocol violation(s) that could affect their PD assessment
PK Evaluable	All participants who complete the EOT Visit and have ≥ 1 evaluable postdose PK assessment

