9.3.10. PK Analyses

Descriptive statistics will be calculated and summarized for plasma and CSF concentrations of IW-6463 at each assessed timepoint.

A population PK approach based on sparse PK data will be used to determine exposure and oral clearance of IW-6463. If data allow, influence of participant demographics (eg, age, race) and effects of concomitant medications on IW-6463 PK exposure will be evaluated. In addition, exposure-effect relationships (such as hemodynamic, biomarkers, and safety parameters) may also be explored. The results of these analyses may be reported separately outside of the clinical study report.

PK parameters of interest include but are not limited to the area under the concentration-time curve from time zero (predose) to 24 hours postdose (AUC_{tau}), time to C_{max} (T_{max}), $t_{1/2}$, maximum observed plasma concentration (C_{max}), plasma concentration observed at the end of a dosing interval (C_{trough}), apparent total plasma clearance (CL/F), apparent volume of distribution (V_z/F), and CSF:plasma concentration ratio, and will be calculated and presented as data permit.

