9.1.1. Dose Reductions or Discontinuations due to TEAE

The number and percentage of participants with study drug dose reductions, or with study drug discontinuations due to TEAE (that is, participants who have a TEAE with a study treatment action taken of “Dose Reduced” or “Drug Withdrawn”) will be summarized for participants in the Safety population. A participant will be counted once if they experienced both these events. Percentages will be calculated based on the number of participants in the Safety population.

All TEAEs lead to study drug dose reductions or study drug discontinuations will be presented in a listing for the Safety population.

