PK samples (Plasma and CSF) will be collected as scheduled in **Table 3**. The actual date and time (24h clock time) of each sample collection will be recorded in the source documents and eCRF.

The lower limit of quantification (LLOQ) for IW-6463 is 1.0 ng/mL. Plasma and CSF concentrations below the limit (BLQ) of quantification will be assigned a value of $\frac{1}{2}$ LLOQ for the calculation of summary statistics and will be presented as BLQ in the listing.

Descriptive statistics for plasma and CSF concentrations of IW-6463 will be summarized for participants in PK Evaluable population at each scheduled assessed timepoint in **Table**

3. The calculation and summary of PK parameters may be described and reported outside of this SAP.

Listings of the plasma and CSF concentrations of IW-6463 data will be provided for participants in the PK Evaluable population.

A population PK approach based on sparse PK data will be used to determine exposure and oral clearance of IW-6463. If data allow, influence of participant demographics (eg, age, race) and effects of concomitant medications on IW-6463 PK exposure will be evaluated. In addition, exposure-effect relationships (such as hemodynamic, biomarkers, and safety parameters) may also be explored. PK parameters of interest include but are not limited to the area under the concentration-time curve from time zero (predose) to 24 hours postdose (AU_{C_{tau}}), time to C_{max} (T_{max}), t_{1/2}, maximum observed plasma concentration (C_{max}), plasma concentration observed at the end of a dosing interval (C_{trough}), apparent total plasma clearance (CL/F), apparent volume of distribution (Vz/F), and CSF:plasma concentration ratio, and will be calculated and presented as data permit.

These analyses will be performed outside of the SAP and reported separately outside of the clinical study report.

12. Pharmacodynamics

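### The PK Evaluable definition requires the EOT Visit, so valid Day 8 and Day 15 levels from a dosed participant without that visit appear in no SAP concentration table or listing

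*SAP*

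**What the plan says.** The population is defined in two places with the same content. SAP 4.3.4 reads "The PK Evaluable population will include all participants who complete the EOT Visit" and then requires at least one usable concentration after dosing. The table in protocol 9.3.2 begins "All participants who complete the EOT Visit and have" and continues with the same second condition. Both conditions must be met.

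SAP Section 11 applies this set to both concentration outputs:

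- Summary table: "Descriptive statistics for plasma and CSF concentrations of IW-6463 will be summarized for participants in PK Evaluable population at each scheduled" time point in SAP Table 3.
- Listing: "Listings of the plasma and CSF concentrations of IW-6463 data will be provided for participants in the PK Evaluable population".

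The exploratory endpoint in SAP 3.2.2 is wider: "Plasma and cerebral spinal fluid (CSF) concentrations of IW-6463 as data permit at assessed timepoints". Protocol 9.3.10 says "Descriptive statistics will be calculated and summarized for plasma and CSF concentrations of IW-6463 at each assessed timepoint" and names no population.

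On participants who stop early, protocol 5.6.2, footnote 2 to protocol Table 1 and the matching footnote in SAP Table 3 ask for the EOT assessments to be done at discontinuation. The request is qualified: where possible in the footnotes, and as appropriate in 5.6.2.

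**The concern.** Plasma samples are scheduled before the EOT Visit. Whether a Day 8 or Day 15 level is valid depends on that sample, its timing and the doses taken before it. It does not depend on whether the participant attends a visit two to three weeks later. The EOT condition nevertheless removes those levels from the table and from the listing.

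Losing them from the listing is the less usual step. A restricted summary can be defended, but a listing normally shows what was measured. Elsewhere the SAP does this: Section 12 lists PD data for the Safety population, and Section 10 summarises and lists the questionnaires on it. SAP 5.1 reports how many participants are excluded from PK Evaluable and why, but not their concentrations.

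What is at stake is completeness of reporting. Protocol 8.6 says "Samples collected for analyses of IW-6463 concentration may also be used to evaluate safety aspects related to concerns arising during or after the study". SAP 9.1.1 says "All TEAEs lead to study drug dose reductions or study drug discontinuations will be presented in a listing for the Safety population". A participant who stopped for a TEAE and had no EOT Visit would have the event in that listing but no concentration in any SAP listing to set beside it.

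**Working it through.** The plan gives no figure to reproduce. The sample size is stated not to rest on statistical considerations (protocol 9.2, SAP 4.1), so no power calculation applies. The check sets the definition against the schedule and the outputs.

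**Inputs**

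- Definition: A and B, where A = completed the EOT Visit and B = at least one usable concentration after dosing (SAP 4.3.4, protocol 9.3.2).
- Outputs limited to that set: the concentration summary and the concentration listing (SAP Section 11).
- Plasma PK schedule: five marks in protocol Table 1 and in SAP Table 3. I read them as Day 8, Day 15, and EOT predose, 2 h and 4 h. Both tables are broken in the text available, so the column reading is an inference. The single CSF mark falls under the EOT columns.

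**Step 1. Who fails.** A participant with no EOT Visit fails A, so A and B fails whatever the value of B. The participant is outside PK Evaluable and appears in neither output.

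**Step 2. How many levels that removes per participant.** Plasma levels scheduled outside EOT = 5 − 3 = 2. Assuming samples are taken as scheduled:

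| Last attended PK sample | Measured levels | Shown in a SAP table or listing |
|---|---|---|
| None (left before Day 8) | 0 | 0 |
| Day 8 | 1 | 0 |
| Day 15 | 2 | 0 |

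The loss is therefore 0, 1 or 2 plasma levels. No CSF level is lost, because CSF is collected only at the EOT Visit.

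**Step 3. Does another provision restore them?**

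- The sentence in SAP Section 12 that lists all Safety participants belongs to the PD section and does not cover concentrations.
- SAP 5.1 gives counts and reasons only.
- Population PK (SAP Section 11, protocol 9.3.10) names no analysis set and may use the levels. SAP Section 11 places that work outside the SAP and the study report.
- An early EOT may bring a participant into the set, but it is a request and cannot help someone who is out of contact (protocol 5.5).

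**Step 4. A side point on B.** The schedule treats assessments as predose unless noted, so the Day 8 and Day 15 samples appear to be taken before that day's dose, though after the first dose. Whether they satisfy B is open to reading. This does not alter Step 1, but it affects how the replacement definition should be worded.

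**Step 5. How many participants.** The documents give no expected number without an EOT Visit. It may be zero.

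**The case against.** The strongest reply is that this is a consistent, prespecified choice. Protocol and SAP give the same definition, and an endpoint says what is measured, not which set is analysed. A reader might infer a protocol–SAP conflict from protocol 9.3.10, which names no population. The documents do not support that: protocol 9.3.2 defines a set called PK Evaluable, and its natural use is the PK analyses. This part of the reply stands, and the point is one of analysis choice.

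The reply also says that the TEAE example is the case best covered, because participants who stop drug are asked to complete the EOT assessments when they stop. That stands too, and it limits the certain exclusions to participants with no EOT Visit at all, in a treatment period of at most 29 days. It does not remove them, because the request is conditional.

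A reader might also infer that safety evaluation is compromised. It is not. Protocol 8.6 permits safety use of PK samples without depending on a SAP listing, the safety analyses use the Safety population, protocol 6.2.2 excludes PK criteria from dosing decisions, and nothing says that the levels are discarded. The gap is in what the SAP outputs display.

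Finally, the SAP does not say whether an early EOT counts as completing the visit, or how its samples map to the Day 29 rows. The separate table and listing specifications (SAP Section 1) may settle both, so neither is counted here. Those specifications should follow the population that the SAP names, so they do not answer the main point.

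**Conclusion.** The point holds and is minor. Under the stated definition, a dosed participant with a valid Day 8 or Day 15 level and no EOT Visit is in no SAP concentration table or listing. The cost is at most 2 plasma levels for each such participant, given the column reading of the schedule and sampling as planned. The number of such participants is unknown and may be zero.

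It is tempting to size this from the plan to dose about 20 participants for about 12 evaluable, and to take the difference, 20 − 12 = 8, as the number at risk. The documents do not support that. They do not define evaluable in that sentence or tie it to PK. The gap could equally reflect the compliance and protocol-violation conditions of the PD Evaluable set, which remove nobody from PK Evaluable. Nor do the documents place any limit on missed EOT Visits, so 8 is neither a forecast nor an upper bound, and percentages built on it would not be evidence of impact.

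PK is exploratory and the primary endpoints are untouched. The reason to act is that a stated rule leaves valid measurements out of the reported outputs and is very cheap to remove.

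**What to change.** Two changes:

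1. In SAP 4.3.4, define PK Evaluable as participants with at least 1 dose and at least 1 evaluable concentration collected after the first dose, without the EOT condition. Align protocol 9.3.2, or record the difference in SAP Section 14. Wording it as after the first dose also settles the status of the Day 8 and Day 15 samples.
2. In SAP Section 11, list all measured concentrations for the Safety population, as SAP Section 12 already does for PD data.

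The second change alone would put the individual levels back on display. The first is needed for them to enter the Day 8 and Day 15 summaries. A participant with no EOT Visit has no Day 29 sample, so admitting such participants leaves the Day 29 rows as they are.

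The cost is two or three sentences in the SAP, plus the aligned protocol definition or one SAP Section 14 entry. No new samples, visits or data collection are needed.
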